Power. This study is powered to estimate the effects of doxazosin on significant reduction in PTSD symptoms at the end of treatment (see Hypothesis 1), and increased abstinence rates at the end of treatment (see Hypothesis 2). Placebo rates of reduction in CAPS scores are conservatively estimated to be 20% (Zohar et al., 2002). In a small pilot study, De Jong et al. (2010) found ~31% reduction in CAPS scores using 4mg doxazosin. A sample of 100 participants will provide 80% power with a .05 type 1 error rate to detect a difference in the reduction of CAPS scores between doxazosin (31±20%) and placebo (20±20%). Placebo rates of drug abstinence are estimated from established double-blind placebo controlled trials. Continuous abstinence from weeks 9-12 is observed in 10-15% of treatment seekers without co-occurring PTSD (Shorter et al., 2013) so we anticipate an attenuated rate of 5-10% in the placebo group. Although there is limited information on the effectiveness of doxazosin in addiction, a sample of 100 subjects (50 in each arm) will provide adequate power to detect an abstinence rate as low as 32% in the doxazosin when the placebo cessation rate is 10% and as low as 23% when the placebo rate is 5%. Due to the nature of the study population, we anticipate ~30% dropout rate; thus the number of subjects randomized is inflated to 144, n=72 randomized to each treatment arm of the study.

Power calculations for the neuroimaging component are based on previous studies of individuals with PTSD or substance use disorders. Based on our previous work and the extant literature, we conservatively estimate that approximately 88/144 will be eligible and volunteer to participate in the neuroimaging component. Of these 88 participants, half (n=44) will be assigned to doxazosin and half to placebo (n=44). Hypotheses 3A and 3B will, therefore, involve the subset of 44 participants who complete the neuroimaging component and receive doxazosin treatment. A recent study of Veterans with PTSD (n=14) as compared to controls (n=15) observed significant differences in PFC-AMY resting state connectivity (Sripada et al., 2012). The effect size for this difference was 0.8 (measured using Cohen's d). Thus, power (1- β) reaches .80 with a total sample size of N=26 (two-tailed, alpha=.05). Another recent study of cocaine-dependent individuals (N=45) found that

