individuals who relapsed (n=24) during treatment had significantly lower PFC-AMY connectivity at baseline as compared to individuals who did not relapse (n=21) (McHugh et al., 2014). The effect size for this reduction was 1.0. Thus, power (1- β) reaches .80 with only 34 total participants (two-tailed, alpha=.05). The present study is therefore well-powered to test the proposed hypotheses.

Missing Data. We will perform attrition analyses on whether participants and dropouts differ on key variables, and whether variables on which they differ interact with treatment to affect outcome measures. As participants will be randomized to treatment, it is unlikely that missing data will produce biased estimates of treatment effect, as observed and unobserved covariates should theoretically be balanced across treatment groups. In addition, in general, less than 10% missing data have little impact on power and do not introduce bias, regardless of the missing data mechanism. Larger proportions of data missing at random (MAR) or missing not at random (MNAR) could potentially bias study findings and reduce power. If the percent missing data are greater than 10%, propensity score methods will be used for data imputation. In the propensity score method, first the distribution of the missing indicator variable given the observed data is modeled to derive a propensity score. Then observations are grouped on these propensity scores and an approximate Bayesian bootstrap imputation is applied to each group.

Hypotheses. The hypotheses and statistical approaches for testing each hypothesis are listed below. An experienced biostatistician at MUSC ([name], Department of Public Health) who has worked with our group for the past five years will collaborate with [name] (Director of the CAP Data Management and Biostatistics Core) as needed during the project to ensure consistency across sites with regard to scoring and analysis of dependent measures.

Hypothesis 1: Participants who receive doxazosin, as compared to placebo, will evidence significantly greater reductions in PTSD severity. To test this hypothesis, generalized linear mixed effects models will be employed to assess reduction in CAPS-5 and PCL-5 total scores during the treatment phase. Restricted maximum likelihood (REML) methods will be used to estimate the fixed effects and variance components, and model based treatment effect estimates will be used to construct group level tests over time.

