Hypothesis 2: Participants who receive doxazosin, as compared to placebo, will evidence significantly greater reductions in SUD severity. To test this hypothesis, logistic regression analysis will be used to examine rates of abstinence (TLFB, biological tests) during the end of treatment phase (week 9-12). Weekly point prevalence abstinence will be examined using generalized linear models under a generalized estimating equations (GEE) framework. GEE models will allow for examination of differential effects of doxazosin vs. placebo on abstinence over the course of the treatment phase of the study. Weekly abstinence (yes/no) as well as amounts (e.g., standard drink units, dollar amount of substances) will be examined over time to determine if treatment is effective in reducing substance use when abstinence is not achieved.

Hypothesis 3A: PFC-AMY connectivity at rest and in response to trauma vs. neutral cues will predict amount of change in PTSD symptoms (CAPS-5).

Hypothesis 3B: PFC-AMY connectivity at rest and in response to substance vs. neutral cues will predict time to first use of alcohol or drugs (TLFB).

The following preprocessing and analytical parameters will be used to test hypotheses 3A-3B. **Preprocessing:** Post-acquisition preprocessing and statistical analysis of all of imaging data will be performed using FEAT (fMRI Expert Analysis Tool) Version 5.98, part of FSL (FMRIB's Software Library). Data will be preprocessed using scripting tools from FEAT. Non-brain signal will be removed using FSL's BET brain extraction. Scans will be corrected for motion using FSL's linear registration and scans will be spatially smoothed using a Gaussian kernel of 8 mm FWHM. Participants with head motion ≥ 0.2 mm will be excluded from the analyses [1]. Motion artifacts will be identified and scrubbed from each subject's data. Scans will be spatially co-registered with a standardized anatomical template (Montreal Neurological Institute) using a 12 parameter affine transformation.

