fMRI Analysis: Functional connectivity will be measured using a PPI seed-based approach [2]. PPI analyses for resting state, trauma and substance cues will be performed separately. Customized sq. wave forms representing the trauma run (1=trauma block and -1=neutral block) and the substance cue run (1=substance block and -1=neutral block) the duration of each block will be convolved with a double-gamma hemodynamic response function. A mask of the seed region will be made using a 12-mm diameter sphere located in the center

of the amygdala using the MNI coordinates (x, y, z = ±22, 0, -22). The transformation parameters described above will also be applied to the mask. For each subject, the mean corrected and high pass filtered time series of the BOLD signal in the AMY will be extracted and used in a single subject whole brain PPI analysis. The PPI model will include the task vector, time series of the BOLD signal in the AMY, a term representing the positive task x seed interaction, and a term representing the negative task x seed interaction. The first level analysis will generate contrast images of the parameter estimates for each of the four regressors. Voxels will be thresholded at $Z>2.3$ using a corrected cluster threshold of $p=0.05$. The contrast images of the parameter estimates of the positive and negative task x seed interactions will be combined for group-level t-tests to identify regions that exhibited altered connectivity with the AMY during the trauma and substance cues as compared to neutral cues. All group-level results will be thresholded at $Z>2.3$ using a corrected cluster threshold of $p=0.05$. Separate linear regression tests will be used to test for associations between PFC-AMY connectivity at baseline and improvement in PTSD and SUD symptoms during treatment. Changes in CAPS-5 total scores will be regressed against the parameter estimate obtained from the center voxel from each cluster that exhibited a significant task x seed interaction with the AMY at rest and in response to the trauma cue (Hypothesis 3A). The number of days to first use (TLFB) will be regressed against the parameter estimate obtained from the center voxel from each cluster that exhibited a significant task x seed interaction with the AMY at rest and in response to the substance cues (Hypothesis 3B).

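### The imaging power statement gives 26 as a total, but 26 is the per-group size (52 in total) at d = 0.8, and neither benchmark powers the regressions planned for Hypotheses 3A and 3B

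*Combined protocol and SAP*

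**What the plan says.** In Statistical Analyses, the second part of the Power section covers the imaging component. It expects that "approximately 88/144 will be eligible and volunteer to participate in the neuroimaging component", split evenly between arms, and then narrows the analysis set: "Hypotheses 3A and 3B will, therefore, involve the subset of 44 participants who complete the neuroimaging component and receive doxazosin treatment".

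Two outside studies are used as benchmarks:

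- A comparison of resting connectivity in 14 Veterans with PTSD and 15 controls, with Cohen's d = 0.8. From this the plan says power "reaches .80 with a total sample size of N=26 (two-tailed, alpha=.05").
- A comparison of baseline connectivity in 24 cocaine-dependent people who relapsed and 21 who did not, with an effect size of 1.0. From this the plan says power "reaches .80 with only 34 total participants (two-tailed, alpha=.05").

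The section then concludes: "The present study is therefore well-powered to test the proposed hypotheses".

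The tests themselves are described under fMRI Analysis: "Separate linear regression tests will be used to test for associations between PFC-AMY connectivity at baseline and improvement in PTSD and SUD symptoms". For Hypothesis 3A, "Changes in CAPS-5 total scores will be regressed against the parameter estimate obtained from the center voxel from each cluster" that shows a significant interaction. For Hypothesis 3B, days to first use is regressed on connectivity in the same way.

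**The concern.** The two totals contradict each other. With the same test, alpha and power, a smaller effect must need more participants, yet the plan asks for 26 at 0.8 and 34 at 1.0. One of them must be wrong, or they come from different methods that the plan does not describe.

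These totals are the only support offered for the conclusion about power, and that conclusion is drawn for 44 participants. A required total of 26 leaves ample room; a total above 44 leaves none.

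The second difficulty is the type of test. A sample size for comparing two means does not give the power of a regression of a continuous outcome on a connectivity estimate, and the plan states no correlation, slope or R-squared for those regressions. At stake is how a null result for 3A or 3B would be read: a reader who relied on the power statement could take it as firmer evidence of no association than the design supports.

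**Working it through.** **Inputs.** All are from the Power section: two-sided alpha .05; power .80; d = 0.8 (groups of 14 and 15); effect size 1.0 (groups of 24 and 21); 44 participants for 3A and 3B. Equal groups are assumed, which both source studies approximate.

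**Method for two groups.** Two-sample t test with n per group: noncentrality d × √(n/2), degrees of freedom 2n − 2, and power from the noncentral t distribution.

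**Step 1: the plan's figure of 34.** At d = 1.0 the solution is n = 16.71, so 17 per group and 34 in total. Check: 1.0 × √8.5 = 2.92 on 32 df gives power 0.807. The figure reproduces exactly as a total.

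**Step 2: the plan's figure of 26, same method.** At d = 0.8 the solution is n = 25.52, so 26 per group and 52 in total.

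| d | Per group | Total | Noncentrality | Power |
|---|---|---|---|---|
| 0.8 | 13 | 26 | 0.8 × √6.5 = 2.04 | 0.499 |
| 0.8 | 22 | 44 | 0.8 × √11 = 2.65 | 0.736 |
| 0.8 | 26 | 52 | 0.8 × √13 = 2.88 | 0.807 |
| 0.8 | 44 | 88 | 0.8 × √22 = 3.75 | 0.960 |
| 1.0 | 17 | 34 | 1.0 × √8.5 = 2.92 | 0.807 |
| 1.0 | 22 | 44 | 1.0 × √11 = 3.32 | 0.900 |

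A rough cross-check: required size scales with 1/d², so the 34 needed at 1.0 becomes 34 × (1.0/0.8)² = 53 at 0.8, close to 52 and far from 26.

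**Step 3: could another method give 26 in total at d = 0.8?** None of those tried does:

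- two-sided normal approximation: 25 per group, 50 in total;
- one-sided t test: 21 per group, 42 in total (26 in total has one-sided power 0.632);
- one-sided normal approximation: 20 per group, 40 in total;
- 14:15 allocation: about 52 in total;
- one-sample or paired t test: 15 two-sided, 12 one-sided.

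Reaching 80% power with 26 in total would need d of about 1.15. A regression with a correlation of 0.5 would have power 0.806 at 26, but the plan states d = 0.8 and no such correlation.

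**Step 4: what 44 gives for the planned test (3A).** For one regression with a single predictor, the smallest correlation detectable with 80% power by Fisher's z is

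r = tanh[(1.960 + 0.842)/√(44 − 3)] = tanh(0.4375) = 0.412.

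Treating the predictor as fixed (noncentral F on 1 and 42 df) gives 0.397. A bivariate-normal simulation of 200,000 runs gives power 0.796 at r = 0.405 and 0.806 at r = 0.41. The answer is therefore about 0.40 to 0.41.

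The number of clusters is not known in advance. As an illustration only, assuming two tests at alpha .025 each, the detectable correlation becomes 0.432 (fixed predictor) to 0.447 (Fisher's z), and power at r = 0.41 falls to 0.717.

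No figure is computed for 3B, because days to first use may be skewed or censored and the normal-theory calculation may not hold.

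**The case against.** The arithmetic is not in dispute; its importance is.

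- **The two halves pull against each other.** If the benchmarks do not apply to the regressions, changing 26 to 52 says nothing about the power of 3A and 3B. If they do apply, the correct figure of 34 still fits within 44. This is fair as far as it goes. But on the plan's own terms one of its two supports fails, and on stricter terms neither is a power calculation for the planned tests. The unqualified conclusion survives neither reading.
- **Power of 0.50 describes a sample the trial never intended.** At 44 split evenly, power is 0.74 at d = 0.8 and 0.90 at d = 1.0. This stands, and it is the better measure of the practical shortfall.
- **The relapse study is close in concept to 3B.** It relates baseline connectivity to relapse. Converting by r = d/√(d² + 4), which assumes an even split, d = 1.0 becomes r = 0.45, with power about 0.87 to 0.90 at 44; d = 0.8 becomes r = 0.37, with power about 0.70 to 0.74 and roughly 55 participants needed. So that benchmark is informative, although it uses a yes/no grouping and not days to first use.
- **All 88 might be analysed.** The General paragraph applies every analysis to all randomised subjects, and the Hypotheses and fMRI Analysis text names no arm. With 44 against 44, power at d = 0.8 is 0.96. However, the Power section is the more specific text and restricts 3A and 3B to the doxazosin arm.
- **The aim is secondary.** Problems and Alternative Strategies says so, and no count or primary analysis changes. This limits the consequence but does not make the figure right.

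**Conclusion.** The concern holds. The stated total of 26 is the per-group size; the correct total is 52, so the figure is wrong by a factor of two. The adjacent 34, correct as a total under the same test, points to a labelling slip and not a different method. This rests only on the plan's stated inputs and near-equal groups.

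Against the 44 participants assigned to 3A and 3B, the d = 0.8 benchmark no longer supports the conclusion, while the benchmark at 1.0 still does. Neither gives the power of the planned regressions.

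The detectable correlation for 3A assumes approximate normality, a single test and 44 analysable participants. The last is not assured, since "Participants with head motion ≥ 0.2 mm will be excluded from the analyses". If, for illustration, the roughly 30% dropout that the Power section expects for the trial also applied to the 44 (44 × 0.70 = 30.8, about 31), the detectable correlation by Fisher's z would be tanh(2.802/√28) = 0.485.

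The consequence is confined to the justification of a secondary aim and the reading of its results. It merits correction because the power conclusion has no other support.

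**What to change.** Make two changes in the neuroimaging part of the Power section.

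1. Replace the total of 26 with 26 per group (52 in total).
2. Replace the concluding sentence on power with text such as:

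> These benchmarks are two-group comparisons of means, whereas Hypotheses 3A and 3B are tested by linear regression. For Hypothesis 3A, 44 analysable doxazosin participants give 80% power to detect a correlation of about 0.40 to 0.41 in a single two-tailed test at alpha = .05, before any allowance for testing several clusters or conditions.

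Make no equivalent claim for 3B unless the calculation allows for the distribution and censoring of days to first use. It would help to add whether the 44 is counted before or after dropout and head-motion exclusions, since the correlation depends on it.

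The cost is a text change. No extra enrolment is needed; the power statement for a secondary aim becomes somewhat less favourable, and 3B carries no power claim until its outcome is considered.

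### The attrition check ignores arm and is nearly blind to dropout whose predictors run in opposite directions in the two arms; randomization does not make up for that

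*Combined protocol and SAP*

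**What the plan says.** The Missing Data paragraph of Statistical Analyses opens with a check in two steps: "We will perform attrition analyses on whether participants and dropouts differ on key variables, and whether variables on which they differ interact with treatment". The sentence ends by naming the target of that interaction: "interact with treatment to affect outcome measures". The first step names no arm. The second step covers only variables that the first has flagged, and it concerns outcome rather than dropout.

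The next sentence gives the reason for not expecting bias: "As participants will be randomized to treatment, it is unlikely that missing data will produce biased estimates of treatment effect". It rests on covariates, observed or not, being balanced between the groups.

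The paragraph then qualifies this: "Larger proportions of data missing at random (MAR) or missing not at random (MNAR) could potentially bias study findings and reduce power". It adds a remedy: "If the percent missing data are greater than 10%, propensity score methods will be used for data imputation". In that method, "first the distribution of the missing indicator variable given the observed data is modeled to derive a propensity score". Neither arm nor arm-by-covariate terms are named for that model.

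The Power paragraph sets the scale: "we anticipate ~30% dropout rate; thus the number of subjects randomized is inflated to 144, n=72 randomized to each treatment arm".

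Hypothesis 1 is tested with a REML mixed model, and Hypothesis 2 with logistic regression and GEE. Neither description names baseline covariates. No section plans a comparison of dropout rate, timing, reason or predictors between arms. DSM Plan Administration lists retention and disposition among the contents of the yearly report, but not by arm or reason.

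**The concern.** Balance from randomization is a property of everyone randomized. It carries over to those who remain only if treatment does not change who leaves. Here it plausibly does. Doxazosin is titrated as tolerated, and Pharmacologic and Clinical Properties lists dizziness in 15% and tiredness in 5–12%. Exclusion criterion 5 says that participants who need new maintenance medication for anxiety, mood or psychotic symptoms may be discontinued, a route that may be commoner where treatment gives no benefit.

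If one arm tends to lose its more severe participants and the other its less severe ones, the two differences offset each other when arms are combined. The first step then flags nothing and the second is not reached, although the remaining groups are no longer comparable. Conversely, if both arms lose the same kind of participant, the pooled comparison fires readily even though the contrast between arms may be undisturbed. With dropout expected at about 30%, the check could reassure or alarm for the wrong reason.

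**Working it through.** **Plan figures first.**
- Sample size: 50 / (1 − 0.30) = 71.4, rounded up to 72 per arm, 144 in total. This reproduces.
- Power, 31 vs 20 with SD 20 and 50 per arm, taken as two-sided 0.05: SE = 20 × √(2/50) = 4; 11/4 = 2.75; 2.75 − 1.96 = 0.79; power = 78.5%. This is close to the stated 80%.
- Expected dropouts: 0.30 × 144 ≈ 43.

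**Inputs to the simulation.** From the Power paragraph: 72 per arm, 30% dropout, 31 vs 20, SD 20. Assumed, because the documents give no values: one standardized baseline variable x; log-odds of dropout with slope −b per SD on doxazosin and +b on placebo, b = 0.4 to 0.7; correlation between x and CAPS reduction of −0.3 to −0.5.

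**Step 1: can the pooled comparison see it?** With equal dropout in both arms, the pooled dropout-minus-completer gap is the average of the two within-arm gaps. At slopes of ±0.5 these are +0.48 and −0.48 SD, so the pooled gap is (0.48 − 0.48)/2 = 0. The pooled t-test then rejects at its false-alarm rate. Detection in each setting:

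| Dropout pattern | Pooled check | Test by arm |
|---|---|---|
| Opposite, ±0.4 to ±0.7, 30% each | 4–5% | about 55–95% |
| Opposite, ±0.5, 30% each | 4.9% | 75% |
| Opposite, ±1, 30% each | 4.2% | 99.8% |
| Opposite, ±1, 40% vs 20% | 12% | 99.6% |
| One arm only, slope 1 | 63% | 65% |
| Same direction in both arms, slope 1 | 99.8% | 5% |

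The first row tests arm-by-baseline on dropout in a logistic model; the others test arm-by-dropout on x. In the last row the completer difference is 11.1 against a true 11: the pooled check fires where the contrast is intact.

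**Step 2: would the second step rescue it?** Only if it were reached. It tests whether x modifies the treatment effect on outcome. In the simulation x has the same slope on outcome in both arms, and this test rejects in about 5% of trials even when run regardless of the first step.

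**Step 3: what can the pattern do to a contrast?** For an unadjusted comparison of completers, bias ≈ correlation × SD × difference between arms in completers' mean x.
- Slopes ±0.4, correlation −0.3: gap about 0.23 SD; −0.3 × 20 × 0.23 = −1.4; 11 − 1.4 = 9.6.
- Slopes ±0.7, correlation −0.5: gap about 0.39 SD; −0.5 × 20 × 0.39 = −3.9; 11 − 3.9 = 7.1.

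Simulated means agree (about 9.6 to 7.1). Reversing the slopes would reverse the sign and overstate the effect. Adding x as a covariate restores about 11.0 in every setting.

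**Step 4: does this carry over to Hypothesis 1?** Not in this form. A REML mixed model was simulated on CAPS at baseline, week 6 and week 12 (the Table 1 schedule), with opposite baseline-driven dropout and assumed scale parameters. The true effect was 4.4. It gave 4.33 (b = 0.4) and 4.46 (b = 0.7), Monte Carlo SE 0.13, against 5.2 and 6.0 from completers. This presumes that baseline CAPS-5 enters the model and is the driver of dropout.

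**The case against.** The strongest reply is that the planned analyses, not the screen, deal with the bias. All randomized participants are analysed, the mixed model uses partial data from those who leave, and imputation is triggered by the percentage missing, which the expected 30% would exceed. No planned analysis depends on the screen's result. This stands. A reader might infer that the screen is the trial's only safeguard, or that the trial would conclude from a clean screen that dropout is harmless; the documents support neither. They call bias unlikely rather than ruling it out, and concede that larger amounts of missing data could cause it.

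It is also fair that the loss of 1.4 to 3.9 points belongs to an unadjusted completer contrast that the plan does not name for Hypothesis 1. The simulated mechanism, baseline severity acting in opposite directions, is assumed; side effects and persisting symptoms arise after baseline. Near-total blindness needs a nearly symmetric pattern: with a slope of 0.7 in one arm only, the pooled check fires in a little over 40% of trials.

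Finally, the text does not say that arms are pooled, and the key variables are undefined. If assigned arm were among them, dropout rates would be compared. Predictors of dropout would still not be compared by arm.

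What the reply leaves untouched is that the other safeguards are not specified well enough to be relied on here. No baseline covariates are named for Hypotheses 1 or 2, and arm is not named in the missingness model. The intention-to-treat sentence defines who is analysed; it does not supply unobserved outcomes.

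**Conclusion.** The concern holds in a limited form. As plainly read, the check has little or no power against dropout whose predictors run in opposite directions by arm: 4–5% under symmetric patterns and 12% in the unequal-dropout case examined. A test by arm reaches about 55–95% for slopes of ±0.4 to ±0.7. The inference from randomization is wrong once treatment can affect who leaves, whatever the size of the effect.

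The fall from 11 to about 9.6–7.1 points shows what the missed pattern can do to an unadjusted contrast under the assumed slopes and correlations. It is not an estimate of bias in the planned mixed model, and it disappears when the driving variable is adjusted for. Harm therefore arises if the driver is unmeasured or left out of the outcome and imputation models. No figure was derived for the abstinence analysis of Hypothesis 2. The point warrants a change to the analysis plan; it does not show that the primary result would be biased.

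**What to change.** In the Missing Data paragraph:

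1. Delete the sentence inferring absence of bias from randomization.
2. Compare the proportion dropping out, time to dropout and recorded reason (side effect, lack of benefit, new medication, other) between arms.
3. Fit a logistic model of dropout on arm, baseline CAPS-5, PCL-5, AUDIT and TLFB, with arm-by-baseline interactions, whatever the pooled comparison shows.
4. Add any baseline variable that predicts dropout in either arm to the Hypothesis 1 and 2 models as a sensitivity analysis.

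The cost is a few extra models on measures already in Table 1 and one reason-for-leaving field on the disposition form. The limitation is power: with about 43 dropouts the interaction test reaches only about 55% at slopes of ±0.4. The plan should say that a null result is not proof that dropout was unselective.
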